Sample size. A meta-analysis of 58 studies indicates that the overall prevalence of postpartum depression is 17% (95% CI: 0.15–0.20) (53). This estimate falls within previously published estimates of 13%–19.2% (54, 55) and is similar to Hahn-Holbrook's 2018 finding of 17.7%. In-person interventions using the *Mother & Babies* course reported moderate effect sizes (OR = 0.28 (0.08-0.94) (22) and OR = 0.45 (0.19-1.10) (24)). Fully web-based without nurse-based telephone support reported small to moderate effect sizes (40). Given that the proposed intervention is offered virtually with nurse-based telephone support, we calculated a sample size that allows us to detect a moderate decrease in rates of clinical depression. We anticipate that 20% of pregnant women in the control group will have an EPDS score ≥ 13 at postpartum. A total of 500 pregnant women (250 per arm) is needed to detect an absolute reduction of 10% (i.e., 20% of women with EPDS ≥ 13 in the control arm versus 10% in the intervention arm) with 80% of power and a 2-tailed alpha of 5%. The sample size includes an attrition rate of 10% for 3 months' postpartum and another 10% between 3 and 6 months' postpartum. Based on our experience with pregnant women and the intervention (see Section about Pilot Study), the 10% attrition estimate is conservative. As most of the secondary

outcomes are continuous, the sample size provides enough power to detect small to moderate effect sizes using a 2-tailed alpha of 1% to account for multiple tests.

Compliance. We conducted a feasibility pilot study including 17 pregnant women. All began to read the online material and 2 refused further participation after 2 telephone calls, a dropout rate of 11.7%. We therefore expect that 80-90% of the intervention group will read at least some of the intervention material. Intervention compliance will be defined as completion of a minimum of 6/8 online modules and 6/10 telephone follow-ups. Compliance will be monitored automatically online and by nurses during telephone calls. Weekly text reminders will be sent out to maximize compliance (see details in Appendix H).

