Duration of treatment period. The typical duration of the program is 2 months (8 weeks) during pregnancy and 2 months over the first 3 months of the baby's life. The two postpartum sessions aim to lend support during the challenges of the postpartum period. The proposed frequency of nurse telephone follow-up is once/week in pregnancy and once/month in postpartum, but this can be adapted to the needs of the woman and/or her partner. Figure 3 presents the intervention and assessments.

Figure 3. Frequency and duration of the follow-up

Participants will fill out questionnaires (online or by telephone) at T₀ (12-25 weeks' gestation), T₁ (3 months' postpartum), and T₂ (6-months postpartum) to assess baseline values and trial outcomes, respectively. If we show efficacy at 3 months' postpartum (primary outcome), we will seek funding to follow families over the early childhood years. Real date of birth will be assessed six weeks after the estimated date of birth.

Coaches training and supervision. PhD students in clinical psychology and Master's students in nursing are ideally suited to conduct the 10 follow-up calls. They will be supervised by our multidisciplinary team (2 nurses, 2 clinical psychologists, and 2 psychiatrists). All coaches will receive 5-day training in perinatal mental health and use of the intervention material. Procedures for calls will be outlined in the intervention manual. The supervision team will oversee implementation as part of the Executive Committee. Intervention sessions will be audiotaped and randomly reviewed by the supervision team to ensure compliance with the material.

Virtual intervention without telephone support (control group). The control group will receive a fully automated version of the virtual intervention

Data Collection

We will conduct a comprehensive assessment of perinatal maternal mental health and functioning as well as factors that may modify the impact of the intervention. The chosen assessment tools are validated (French and English), require low levels of literacy and take only 15-30 minutes to complete (Appendix L, Description of assessment tools). They have been used previously with pregnant women and examined for clarity, comprehension, and ease of use. The questionnaires will be completed online via REDCap or over the telephone with a research assistant blinded to group allocation depending on maternal preference, and with the partner if the woman so chooses.

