Secondary outcomes. Participant and partner assessments at baseline, T₁ and T₂. The proposed intervention is based on CBT principles used to treat both anxiety and depression. As anxiety is highly correlated with perinatal depression, it is an important secondary outcome. **Generalized anxiety.** The proposed intervention is based on CBT principles used to treat both anxiety and depression. As anxiety is highly correlated with perinatal depression, it is an important secondary outcome. Anxiety will be assessed at all 3 time points, using the Generalized Anxiety Disorder 7-item (GAD-7) scale, an extensively validated self-report instrument (75-77). **Anxiety related to pregnancy** will be measured with the 10-item Pregnancy-specific anxiety scale (PRAQ-R2) (78, 79) at baseline. **Stress** will be assessed using the 10-item form of the Perceived Stress Scale, at six months postpartum (80, 81). **Well Being** will be evaluated with the 5-item WHO-5 well-being index at T₁ (82). **Self-efficacy** will be assessed using the 10-item General Self-Efficacy Scale (GSE) at 3 months postpartum (83, 84). **Self-Compassion** will be measured with the 12-item shortened version of the Self-Compassion Scale (SCS) (85-87), at 3 months postpartum. **Sleep.** Sleep may improve as a result of the increased capacity for relaxation, mindfulness, and emotional regulation fostered by the intervention. At 3 months postpartum, we will assess sleep quality, a critical aspect of perinatal maternal health, using the 19-item Pittsburgh Sleep Quality Index (PSQI) (88, 89), a self-report over a one-month interval with very good psychometric properties and validated for use during postpartum (90). **Tobacco, alcohol and drug use** will be self-reported at baseline and 3 months postpartum. **Social Adjustment** will be assessed using the 14-item screener version of the Social Adjustment Scale – Self-report (SAS-SR) (91, 92). Six major areas are covered: work (paid or unpaid), social and leisure activities, relationships with extended family, role as marital partner, role as a parent, and role within the family unit (including perceptions about economic functioning). For this study, we will only use the work subscale at 3 months postpartum. **Marital satisfaction** will be evaluated with the short version of the Dyadic Adjustment Scale (DAS-7) (93-95) at 3 months postpartum. **Co-parenting.** The proposed intervention is partner-inclusive and, as such, may improve co-parenting quality (the extent to which parents work together and agree on childcare and education). We will use a brief 14-item version of the Coparenting Relationship Scale (75) (e.g., partner pays a great deal of attention to our child; partner appreciates how hard I work at being a good parent) at 3 months postpartum. **Social Support** will be assessed at 6 months postpartum using the 10-item Social Provisions Scale (SPS-10) on emotional

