Economic evaluation. Service utilization will be measured using a slightly modified version of the **Health Service Utilization and Cost of Care Questionnaire** (105) to assess childcare expenses and travel costs incurred by patients to obtain care. Costs of administering the intervention include a) recruiting and training of nurses, b) nurses' time to provide the intervention, and c) supervision of nurses.

Planned Analyses

Data will be analyzed using SAS software using an intent-to-treat approach. A two-sided significance level of 0.05 will be used for the primary outcome; a significance level of 0.01 (two-sided) will be used for secondary and other outcomes to account for multiple outcomes. Demographic and other baseline variables will be compared between study groups using descriptive statistics (mean, standard deviation, proportions).

For the primary outcome, a two-sample sided test of proportion (chi-square test) will be used to compare the difference in the proportion of women with EPDS in the clinical range (> 13) at 3 months' postpartum. The same approach will be used for the 6-month assessment (secondary outcome). These analyses will be supplemented by an analysis using EPDS scores, where the baseline EPDS score will be used as covariate in an ANCOVA model including the 3- and 6-month EPDS scores. With this model, we will obtain 95% confidence intervals of EPDS score differences between intervention arms at 3 and 6 months' postpartum. Sensitivity analyses will be performed to investigate the potential bias introduced

by attrition. A method based on inverse-probability-of-attrition weights (IPAWs) will be used (101, 102).

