For secondary outcomes, the statistical method for comparing intervention arms will depend on the distribution of the outcome variable. For binary variables, chi-square tests will be used. The corresponding 95% CI for the difference in proportions will also be provided. In the unlikely event that randomized intervention arms are unbalanced for baseline variables known to be associated with primary and secondary outcomes, logistic regression will be used where unbalanced variables will be included. For continuous variables, we will use ANCOVA models as described above. Again, unbalanced variables will be added if needed. If the intervention is found to be effective, exploratory analyses will be conducted to explore the potential effect of moderator variables using causal inference models including gender and intervention compliance (103, 104). No formal interim efficacy analysis is planned. Ethical practices and conduct of the trial as well as all safety concerns will be reported to an independent Data and Safety Monitoring Committee.

Planned subgroup analyses. The ANCOVA models presented above will be expanded to include the socioeconomic status of the participant, ethnicity, personality disorder symptoms subgroup variable as well as interaction with the intervention.

Pilot Study

We conducted a feasibility study to assess acceptability and compliance to the intervention (n = 17). Pilot data indicate that women used a mix of electronic devices to access the intervention. All used an iPad at some time, 40% also used their smartphone and 20% also used a computer. Telephone follow-up by a nurse was rated as “essential” (40%), “very useful” (40%), or “useful” (20%). Online sessions were rated as “very useful” (60%) or “useful” (40%). Strategies proposed in the intervention (cognitive restructuring, relaxation, behavioral modification, social support) were used “regularly” (30%), “often” (50%), “occasionally” (10%), or “never” (10%). The material was rated as “very easy to understand” (90%) or “easy” (10%). Each strategy was used at least occasionally by 86% of women. Qualitative data indicated high levels of appreciation (Appendix A).

Ethical considerations

Voluntary informed consent

The recruiting process will allow women to give a voluntary informed consent (Appendix E). The consent form will be signed on the online platform provided by the URCA.

Confidentiality and Privacy Protection

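### Eight secondary scales that could be answered in pregnancy are listed at one postpartum visit only, so on those entries their ANCOVA has no own-baseline covariate; the cost is precision, not validity

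*Combined protocol and SAP*

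**What the plan says.** **Model.** Planned Analyses describes one ANCOVA, for the EPDS score, "where the baseline EPDS score will be used as covariate in an ANCOVA model". For the continuous secondary outcomes it then says "For continuous variables, we will use ANCOVA models as described above", with unbalanced variables added if needed. No covariate is named scale by scale.

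**Timing, general statements.** The Secondary outcomes paragraph opens with "Participant and partner assessments at baseline", T1 and T2. The text on assessments under Duration of treatment period says that questionnaires at T0, T1 and T2 serve "to assess baseline values and trial outcomes, respectively".

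**Timing, scale by scale.** The entries in the Secondary outcomes paragraph are narrower. Stress "will be assessed using the 10-item form of the Perceived Stress Scale, at six months postpartum"; social support (SPS-10) is also listed at 6 months only. WHO-5, self-efficacy (GSE), self-compassion (SCS-12), sleep (PSQI), the SAS-SR work subscale and marital satisfaction (DAS-7) are listed at 3 months only. The same paragraph does name baseline for other measures: GAD-7 at all three visits, PRAQ-R2 at baseline, substance use at baseline and 3 months.

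**Error level and power.** Planned Analyses states that "a significance level of 0.01 (two-sided) will be used for secondary and other outcomes to account for multiple outcomes". The Sample size paragraph says that "the sample size provides enough power to detect small to moderate effect sizes using a 2-tailed alpha of 1" per cent, without giving an effect size, a power or a baseline correlation.

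**The concern.** An ANCOVA gains precision when the covariate predicts the outcome, and the best single predictor is usually the same scale measured before treatment. If the scale-by-scale entries describe what is collected, eight outcomes have no such covariate. The only one the plan carries over is the eligibility EPDS, and the inclusion criteria restrict that to four score values.

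Two things are then lost. Stable differences between women in stress, support, marital satisfaction and so on stay in the error term, while the test is held to the 1% level. And the plan's own safeguard, adding baseline variables found to be unbalanced, cannot be applied directly to a scale that was not measured at T0. A baseline that was not collected cannot be recovered later.

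**Working it through.** **1. The plan's own figure.** Inputs from Sample size: 20% versus 10%, two-sided 5%, 80% power, 10% attrition by 3 months and another 10% by 6 months.

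n per arm = [1.96·√(2·0.15·0.85) + 0.842·√(0.20·0.80 + 0.10·0.90)]² / 0.10² = 199 (no continuity correction).

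199/0.80 = 249 and 199/0.81 = 246 (rounded up). The stated 250 per arm reproduces.

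**2. Women available for the secondary scales.** 250 × 0.90 = 225 per arm at 3 months. 250 × 0.90 × 0.90 = 202.5, taken as 202, at 6 months.

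**3. How much the eligibility EPDS can do.** Assume scores spread evenly over 9–12: SD = √((16 − 1)/12) = 1.12. Assume an unrestricted EPDS SD of 4 to 6 and an unrestricted correlation r of 0.3 to 0.7 with the outcome. With u = 1.12/SD, the correlation within the restricted range is

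r·u / √(1 − r² + r²·u²),

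which runs from 0.06 (r = 0.3, SD 6) to 0.26 (r = 0.7, SD 4). The variance removed is the square, about 0.3% to 7%. At r = 0.5 and SD 5 the restricted correlation is 0.13, and power for a 0.30 SD effect at 3 months moves only from 72.8% to 73.7%.

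**4. What an own baseline would do.** Two-sided alpha 0.01, 80% power:

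detectable difference (SD) = (2.576 + 0.842)·√(2/n)·√(1 − r²)

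power for d = Φ(d·√(n/2)/√(1 − r²) − 2.576)

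Here r is the correlation of the T0 score with follow-up. The documents give no value, so a range is shown.

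| Assumed r | 3 months, n = 225: detectable | Power for 0.30 SD | 6 months, n = 202: detectable | Power for 0.30 SD |
|---|---|---|---|---|
| 0 (no useful covariate) | 0.322 | 72.8% | 0.340 | 67.0% |
| 0.3 | 0.307 | 77.6% | 0.324 | 72.1% |
| 0.5 | 0.279 | 86.4% | 0.294 | 81.7% |
| 0.6 | 0.258 | 91.9% | 0.272 | 88.4% |

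The 3-month columns apply to WHO-5, GSE, SCS-12, PSQI, the work subscale and DAS-7. The 6-month columns apply to PSS-10 and SPS-10. The equivalent sample factor is 1/(1 − r²): 1.10, 1.33 and 1.56 for r = 0.3, 0.5 and 0.6.

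**5. When T0 would be answered.** Under Pregnant Women Recruitment, eligible women are randomised and told their group. The text closing Partners Recruitment then sends the baseline questionnaire link, and website access opens once it is completed. As written, T0 scales would precede use of the online material but follow knowledge of the arm. The eligibility EPDS is taken before randomisation and does not have this problem.

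**The case against.** **The scales may already be in the T0 form.** The lead-in and the T0/T1/T2 sentence both point to baseline collection, and the places that would settle it (Appendix E, Appendix L, Figure 3) are not in the text. A reader might infer that these eight scales certainly have no baseline; the documents do not support that. They support a conflict in which the specific entries are the more coherent reading, because the same paragraph names baseline where it means it. Either way the text needs correcting.

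**The ANCOVA is not formally unadjusted.** Taken literally it carries baseline EPDS and allows unbalanced variables to be added, and GAD-7 at T0 is a related measure. This stands. That EPDS removes little variance is an inference from the 9–12 range and assumed correlations.

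**The gain may be small.** T0 is at 12–25 weeks. Assuming birth at 40 weeks, T1 comes about 28 to 41 weeks later and T2 about 41 to 54, with a birth in between, so correlations could be modest and lower at T2. This stands, and is why r = 0.3 is shown.

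**Nothing stated is refuted.** A reader might infer bias in the secondary comparisons, or that the power sentence is wrong. Neither follows: randomisation protects the comparison without any baseline, and 0.32 to 0.34 SD still fits a loose description of small to moderate. Leaving scales out of T0 to limit burden is also a legitimate choice, provided the plan says so.

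**Conclusion.** The point holds as a matter of efficiency and internal consistency. The lead-in and the scale entries disagree, and on the entries the named ANCOVA has no own-baseline covariate for eight scales. The primary analysis is untouched and the secondary comparisons remain valid.

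The loss is about 0.02 to 0.06 SD in detectable difference at 3 months and 0.02 to 0.07 SD at 6 months. For a true 0.30 SD effect that is about 5 to 19 points of power at 3 months and 5 to 21 at 6 months. Chance imbalance on the scales themselves also cannot be checked. These sizes rest on assumed correlations of 0.3 to 0.6, the planned attrition, and a negligible contribution from the restricted EPDS. They are for the women: partner numbers are not given, and partner eligibility sets no EPDS range.

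**What to change.** - Reconcile the lead-in of Secondary outcomes with its entries by adding at least WHO-5 (5 items), DAS-7 (7), PSS-10 (10) and SPS-10 (10), 32 items in all, to the existing T0 questionnaire for women and participating partners.
- Have that questionnaire completed before allocation is disclosed, and amend the recruitment text accordingly. Partners absent from the recruitment call are approached later, so state the sequence for them explicitly.
- In Planned Analyses, state that each such outcome is analysed by ANCOVA on its own T0 score.
- For any scale left without a T0 measure (GSE, SCS-12, PSQI and the work subscale under this minimum), state that no own-baseline adjustment is made and which covariate, if any, is used. Co-parenting, ÉCOPAN, ASQ-3 and ICQ concern an infant already born and stay follow-up only.

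Cost: a somewhat longer baseline form, an edit to the REDCap questionnaire and a text amendment; no extra visit and no larger sample size. Moving the form ahead of disclosure means that women who do not return it would not proceed to allocation, which may slow recruitment slightly. If T0 collection is already intended, correcting the entries, settling the order and naming the covariates is enough.

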Pregnant women will be recruited via three possible means: 1) Recruitment posters and pamphlets (Appendix B, Recruitment poster and pamphlet) distributed in clinics associated with the CHU Ste Justine; 2) Obstetrician, psychiatrists or general practitioner in clinics associated with the CHU Ste Justine; or 3) Advertisements posted on various social media (Facebook, Instagram; Twitter, etc.). Interested women will either 1) connect to a web page and fill a contact form (Appendix C); or 2) contact us by phone, text message or email.

The research coordinator will contact women referred by practitioners or through advertisement. The study will be explained and a consent form (Appendix F, Consent forms) will then be sent through REDCap. Participants will sign virtually. Then, they will respond by telephone to the eligibility questionnaire (5 min.), including the EPDS (50) psychosis screening questionnaire and self reported substance abuse problem. Those with subclinical levels of depression (EPDS 9-12) and without psychosis and substance abuse problem will be randomized via REDCap and informed of their group allocation.

Partners Recruitment

During the recruitment phone call with pregnant women, the research coordinator will explain the possibility of partners to participate in the study and the advantage of it. A partner can be the spouse or any other significant person who will accompany the pregnant woman during pregnancy and after childbirth. It is recommended to keep the same person for the duration of the course. The research coordinator will ask the pregnant women to identify her partner and if he or she is at home at this moment, he or she will be invited to join the call. Partners will be eligible only if the pregnant woman signed the consent form and is eligible for the study. If the partner is absent, the research coordinator will ask for his or her email or telephone number. If the pregnant woman sign the consent form and is eligible for the study, an invitation will be sent to briefly explain the project and to ask them if they accept us to call them to give more information and recruit them if interested. The research coordinator will then contact those interested, explain the study and send an email with the consent form.

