Counseling interventions received a grade B recommendation from the USPSTF (2), reflecting the low level of risk and high probability of a moderate net benefit. None of the included studies, however, offered virtual counseling and there is very little evidence of the efficacy of virtual prevention interventions. As in all studies where participants report on their mental health, there is always the possibility that participants become more aware of their symptoms. We will minimize risk to participants by taking the following measures. First, at the end of each assessment, there will be a list of resources to manage mental health issues (Appendix M). The list will include contact information for: 1) in Quebec, Integrated University Health and Social Services Centres (CIUSS). These local community health centers offer prenatal classes, telephone call services, and links to psychosocial and mental health services; 2) family physician clinics; 3) obstetric clinics, and; 4) emergency phone numbers and help lines. Second, we will set up a telephone line to answer questions about the study and remind participants of available resources. Third, participants with a positive response on the EPDS self-harm ideation item or scoring above the clinical EPDS cut-off (≥ 13) during screening or follow-up will be notified by a pop-up at the end of the questionnaire. The pop-up will inform them they will receive a phone call from a nurse of our team and encourage them to speak to their doctor and contact resource links (Appendix N). The nurse will make the call within 24 hours to evaluate the suicidal risk and make sure the participant is taken in charge by appropriate health services.

Expected Results and Benefits

[figure not shown]
This project will 1) provide virtual support related to the program content to women with symptoms of depression (moderate severity) in a context where individual medical and psychosocial follow-ups are minimized due to the pandemic; 2) prevent the worsening of depression and anxiety, improve stress management, and potentially improve obstetric outcomes and prevent child development disorders associated with maternal disorders; 3) develop an online economic intervention for pregnant women in situations of social isolation or activity limitations due to various causes (e.g., pandemic, strict rest at home); 4) facilitate the coordination of virtual social support by maternal and child physical health specialists and

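### In online follow-up, the self-harm / EPDS ≥ 13 pop-up and the resource list are placed at the end, so a woman who gives an alarming answer and then stops early may see neither at that visit

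*Combined protocol and SAP*

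**What the plan says.** All of the safeguards are described in the protocol under Ethical considerations, Risks to Participants.

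- **Resource list:** "at the end of each assessment, there will be a list of resources to manage mental health issues".
- **Telephone line:** "we will set up a telephone line to answer questions about the study and remind participants of available resources".
- **Alert:** it covers "participants with a positive response on the EPDS self-harm ideation item or scoring above the clinical EPDS cut-off" (13 or more), at screening or follow-up. These women "will be notified by a pop-up at the end of the questionnaire".
- **Content of the alert:** "The pop-up will inform them they will receive a phone call from a nurse of our team". It also encourages them to speak to their doctor and use resource links.
- **Nurse's call:** "The nurse will make the call within 24 hours to evaluate the suicidal risk".

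Data Collection says that the assessment tools "take only 15-30 minutes to complete" and may be answered online or by telephone with a blinded assistant, as the mother prefers. Pregnant Women Recruitment describes screening as a telephone "eligibility questionnaire (5 min.), including the EPDS". The text reviewed gives neither the order of the scales nor any rule for a partly completed form.

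**The concern.** Both on-screen measures are tied to reaching the end of something, and nothing ties them to the moment the EPDS answers are given. The EPDS is one of many scales in a battery that may take half an hour. A woman who has just endorsed self-harm, or whose answers put her in the clinical range, may close the browser before the remaining scales. She would then miss the notice that a nurse will call, the advice to contact her doctor, and the list of services.

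What is at stake is participant safety for a small number of women. The primary analysis, the power and the sample size are not affected.

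**Working it through.** The plan gives no figure on this point to reproduce. The check is a reading of the text, followed by a rough scale.

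**Step 1: what *questionnaire* means.** Usage is mixed. Pregnant Women Recruitment has an eligibility questionnaire that contains the EPDS, and the text on partner recruitment has a baseline questionnaire for the whole set; both are batteries. But the protocol also uses the word in the names of single instruments: the psychosis screen, the child-development and infant-temperament measures, and the service-use form. The battery reading is the more natural one for the pop-up sentence, but it is not certain.

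**Step 2: what an early stopper misses under each reading.**

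| Situation at follow-up | Pop-up | Resource list |
|---|---|---|
| Online; *questionnaire* is the EPDS form alone | seen | missed |
| Online; *questionnaire* is the battery, EPDS last | nearly always seen | nearly always seen |
| Online; *questionnaire* is the battery, EPDS not last | missed | missed |
| By telephone | a research assistant is on the line | a research assistant is on the line |

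Only the third row gives the full gap. It needs both the battery reading and an EPDS that is not last.

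**Step 3: scale at 3 months.** Inputs from Sample size: 250 women per arm, 10% attrition by 3 months, and EPDS ≥ 13 in 20% of the control arm and 10% of the intervention arm.

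- Women assessed per arm: 250 × 0.90 = 225.
- Women at or above 13: 225 × 0.20 + 225 × 0.10 = 45 + 22.5 = 67.5.

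The documents give no rate of stopping between the EPDS and the end of the battery, so the following rates are assumptions:

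- 1%: 67.5 × 0.01 = 0.7 women
- 5%: 67.5 × 0.05 = 3.4 women
- 10%: 67.5 × 0.10 = 6.8 women

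These figures treat every assessment as online. Any telephone share lowers them in proportion, and that share is not given. Women below 13 who endorse the self-harm item would be additional; their number cannot be derived from the documents.

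**The case against.** The strongest reply is that the main safeguard is the nurse's call, not the screen. The women to be called are defined by their answer or score, and nothing in the text makes the call depend on finishing. This stands. A reader might infer that a woman who stops early also gets no call, but the documents do not support that. They leave open whether a saved answer or a completed form sets the call in motion.

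A reader might also infer that the resource list reaches only women who finish each follow-up. That goes too far. Access to the intervention website is granted only after the baseline questionnaire is completed, so a woman given access should already have reached the list once. The telephone line is a further route, although as described she has to ring it herself. What she loses at follow-up is a repeat of the list and the advance notice and advice in the pop-up.

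Three further points stand. Screening is a short telephone call with staff on the line, so the gap belongs to online follow-up. An EPDS placed last would almost close it. The appendices with the questionnaires, the list and the pop-up links are not in the text reviewed and may hold display details.

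Adding the 6-month visit would also invite a larger count. If the same rates persisted (an assumption), 250 × 0.80 = 200 per arm gives 200 × 0.20 + 200 × 0.10 = 60 more. These are woman-visits, because the same woman can score high twice, so the sum should not be read as a number of women.

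None of this removes the core point. The protocol text permits a sequence in which a flagged woman sees neither measure at that visit, and it does not say how partial responses are handled.

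**Conclusion.** The point holds in a limited form. For follow-up completed online, and provided that *questionnaire* means the battery and the EPDS is not last, a woman who gives an alarming answer and stops early sees neither the pop-up nor the list at that visit. On the planning rates and an assumed 1-10% break-off, this affects about 1-7 of some 67 women with EPDS ≥ 13 at 3 months, fewer with telephone completion. The break-off range has no source in the documents and serves only to show the order of magnitude.

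The finding does not show that the nurse's call fails, or that these women never receive the resource information. It is a gap in the on-screen display and an unstated trigger, worth closing because the remedy is so cheap.

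There is also one inconsistency to settle. Risks to Participants provides for a pop-up during screening, while Pregnant Women Recruitment has screening done by telephone.

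**What to change.** In Risks to Participants, replace the end-of-questionnaire placement with a sentence to this effect: the existing pop-up (for women who meet the existing criteria) and the resource list are displayed once the EPDS page has been saved, whether or not later scales are completed, and the list is shown again at the end of the assessment. Put the EPDS on its own REDCap page so that its answers are saved separately.

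Leave the alert criteria and the nurse's call as they are. Ask the sponsor to state whether the call is set in motion by saved answers or by a completed form, and to reconcile the pop-up during screening with telephone screening. If the REDCap build or the appendices already provide for this, one confirming sentence in the body is enough.

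The cost is a sentence and a REDCap setting. The downside is that a few women may stop after the pop-up and leave later secondary scales blank. The EPDS answers, and so the primary outcome, would already be saved.
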